- Aetna Compassionate Care Program (ACCP) participants – individuals with advanced illness and limited life expectancy

Through the use of the above inclusion and exclusion criteria, but not excluding patients with a diagnosis of atrial fibrillation or flutter, we expect to identify a population with an overall prevalence of known AF of 10-15%. Based on prior studies supporting that 30% of the total AF population is undiagnosed, then the total AF population (X) = diagnosed AF population (0.7X) + undiagnosed AF population (0.3X). Therefore with a 12% prevalence of diagnosed AF representing only 70% of the total AF population that would suggest that the true total AF population prevalence is 17%, and therefore the prevalence of undiagnosed AF would be ~5%.

[figure not shown]
Participant Recruitment

Eligible Aetna members will be contacted by letter, electronically or paper, (Appendix 1) with information about the study and an invitation to learn more via a study-specific web site as well as the option to discuss with a research coordinator. Once an individual agrees to participate they will be directed to an online Informed Consent Document, or if they prefer, one will be mailed to them.

A conservative estimate is that 5% of the approached population will agree to participate in the study. With an estimated >100,000 eligible participants to approach this should allow for the recruitment of a total of 2000 individuals for randomization and allow for development of a matched observational cohort of 4000 individuals.

It is anticipated that 10,000 invitations will be sent out to eligible Aetna members on a rolling basis every one to two weeks with invitations continuing until ~2250 (to account for an assumed 12% drop-out in first year) individuals have agreed to participate and signed the informed consent.

Study Flow

Randomized Cohort

Following informed consent individuals will be randomized to either the immediate screening arm or the delayed screening arm. All individuals randomized to immediate screening will be sent their monitoring device(s) immediately after signing their informed consent. Their 4 months of monitoring will begin the first day their monitoring device is activated. Those randomized to delayed monitoring will receive their monitoring device(s) 4 months after the date of their informed consent being signed, with their 4 months of monitoring also starting the first day their monitoring device is activated.

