become more ubiquitous in wearable mHealth devices. Data is analyzed on a near-continuous basis for rhythm abnormalities as well as other physiologic parameters. Individuals agreeing to be monitored with the Amiigo will have one sent to them along with a charging device and instructions to download the smartphone app. Only routine fitness data, such as activity, calories burned and sleep duration will be available to Amiigo users via the app. Individuals will be encouraged to wear the device as frequently as possible, night and day, throughout the 4-month monitoring period. Rhythm monitoring will occur passively while a subset will also be prompted daily to sit quietly for 60 seconds to allow for active monitoring. As the Amiigo's rhythm detection capability is exploratory anyone identified to potentially have AF during a period when they are not concurrently wearing a ZIO XT Patch, will be sent another ZIO XT Patch to wear for an additional 2 weeks in order to confirm the diagnosis of AF.

Observational Control Group

A risk-matched observational cohort will be developed from among individuals deemed eligible for study participation but not having the opportunity to participate in the randomized study (i.e. randomized cohort filled prior to their being invited). Individuals will be matched 2:1 with the 2,000 actively monitored cohort based on age, gender, CHA₂DS₂-VASc score, and Propensity Score. An individual's CHA₂DS₂-VASc score can range from 0 to 10 and is based on the composite value of points determined by the presence of cardiac failure or dysfunction (1 point), Hypertension (1 point), Age \geq 75 (2 points), Diabetes (1 point), Stroke (2 points)-Vascular disease (1 point), Age 65–74 (1 point) and Sex category (1 point for female).

The observational period of controls will begin the day their matched actively monitored counterpart signed their informed consent.

Atrial Fibrillation Diagnosis

In the actively monitored cohort a diagnosis of atrial fibrillation/flutter will be made based on documented evidence of a minimum of 30 seconds of continuous atrial fibrillation or flutter confirmed by ECG monitoring with the ZIO XT Patch during the active monitoring period, or the new clinical diagnosis of atrial fibrillation or flutter based on claims data. For the control cohort a new diagnosis will be based solely on a new clinical diagnosis documented in claims data.

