3. ANALYSIS OBJECTIVES

The analysis objectives corresponding to the study objectives listed in 1. INTRODUCTION AND BACKGROUND are the following:

Primary Analysis

1. Compare incidence of newly diagnosed atrial fibrillation (as defined by ≥ 30 seconds of atrial fibrillation or flutter detected by device, or a new clinical diagnosis recorded in claims data) at the end of the 4-month monitoring period in the immediate monitoring cohort (n=1,000) with delayed monitoring cohort (control group) (n=1,000) using ICD-9/ICD-10 codes.

Secondary Analyses

1. Compare time to first event of newly diagnosed atrial fibrillation (as defined by ≥ 30 seconds of atrial fibrillation or flutter detected by device, or a new clinical diagnosis recorded in claims data) at the end of the 4-month monitoring period in the immediate monitoring cohort (n=1,000) with delayed monitoring cohort (control group) (n=1,000) using ICD-9/ICD-10 codes.
2. Compare incidence of newly diagnosed atrial fibrillation (as defined by ≥ 30 seconds of atrial fibrillation or flutter detected by device, or a new clinical diagnosis recorded in claims data) at the end of the 4-month monitoring period in the immediate monitoring cohort (intervention group) (n=1,000) with delayed monitoring cohort (control group) (n=1,000) using HPD definition.
3. Compare prevalence of atrial fibrillation in the actively monitored cohort (n=2,000) with the matched observational control cohort (n=4,000) at 12 months.
4. Compare time to event of newly diagnosed atrial fibrillation in the actively monitored cohort (n=2,000) with the matched observational control cohort (n=4,000) at 12 months.
5. Compare the rate of initiation of anticoagulation therapy in the actively monitored cohort with the matched observational control cohort at 12 months.
6. Compare the rate of initiation of other atrial fibrillation-related therapies (antiarrhythmic agents excluding beta-blockers and calcium channel blockers, cardioversions, ablation procedures or hospitalizations with a primary diagnosis of AF) in the actively monitored cohort with the matched observational control cohort at 12 months.
7. Compare utilization in actively monitored cohort with the matched observational cohort at 12 months.
8. Compare time to first event of the combined endpoint of stroke, systemic embolism, or myocardial infarction in the actively monitored cohort with the matched observational control cohort at 3 years:

- a. In the entire cohorts.

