- b. In the sub-population of individuals newly diagnosed with AF during the 3-year follow-up.

9. Compare time to first event of the combined endpoint of stroke, systemic embolism, myocardial infarction or death among subjects in the Medicare population at baseline in the actively monitored cohort with the matched observational control cohort at 3 years:

- a. In the entire cohorts.
- b. In the sub-population of individuals newly diagnosed with AF during the 3-year follow-up.

10. Compare time to first event of individual components of the combined endpoint (stroke, systemic embolism, myocardial infarction) in the actively monitored cohort with the matched observational control cohort at 3 years:

- a. In the entire cohorts.
- b. In the sub-population of individuals newly diagnosed with AF during the 3-year follow-up.

11. Compare time to first event of all-cause hospitalizations in the actively monitored cohort with the matched observational control cohort at 3 years:

- a. In the entire cohorts.
- b. In the sub-population of individuals newly diagnosed with AF during the 3-year follow-up.

12. Compare total number of all-cause hospitalizations in the actively monitored cohort with the matched observational control cohort at 3 years:

- a. In the entire cohorts.
- b. In the sub-population of individuals newly diagnosed with AF during the 3-year follow-up.

Analysis of Safety Endpoints

1. Compare time to first event of hospitalization for a primary bleeding diagnosis in the actively monitored cohort with the matched observational control cohort at 3 years:
 - a. In the entire cohorts.
 - b. In the sub-population of individuals newly diagnosed with AF during the 3-year follow-up.
2. Compare incidence of the detection of non-AF, but other actionable heart rhythm issues during monitoring in the actively monitored cohort with the matched observational control cohort in the entire cohorts at 3 years.
3. Describe incidence, timing and etiology of discontinuation of active monitoring in the monitored cohort.

Exploratory Analysis

1. Evaluate the correlation between AF detected by the Amiigo wristband with the incidence of AF detected by the Zio patch in active monitoring cohort during 4 months of active monitoring.

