For the Matched Observational Cohort Study, the ITT population will be all subjects enrolled in the RCT (actively monitored group=immediate monitoring + delayed monitoring) and their matched controls. The per protocol analysis will consist of 1) all subjects in the RCT had analyzable data from Zio patch monitoring of at least 30 continuous minutes during the RCT and who did not request removal from the observational follow-up at time of withdrawal and 2) their matched controls.

Matched Observational Cohort Study: Atrial Fibrillation Sub-population

The sub-population of subjects diagnosed with atrial fibrillation for the analyses of disease endpoints and hospitalization events will consist of subjects in the actively monitored group who received a new diagnosis of atrial fibrillation during active monitoring with the Zio patch or at any time during the 3 year follow-up by claims data and subjects in the matched observational control cohort who received a new diagnosis of atrial fibrillation based on claims data during the 3 year follow-up.

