5. ENDPOINTS AND COVARIATES

[Data source in brackets]

Primary Endpoint

1. Atrial Fibrillation/Flutter: new diagnosis of atrial fibrillation or atrial flutter defined as:
 - a. ≥ 30 seconds of atrial fibrillation or flutter diagnosed and adjudicated on the iRhythm output (monitored cohort) [PI Diagnosis Database]
 - i. Date
 - ii. Duration
 - b. Claim for atrial fibrillation/atrial flutter with ICD-9 code 427.1 or 427.2 or ICD-10 code I48.91 or I48.9 [Aetna Claims Data; Aetna Medical Case]
 - i. Date

Secondary Endpoints

1. Atrial Fibrillation/Flutter: HPD algorithm [Aetna HPD Database]
2. Anticoagulation: Drug NDC codes for new refill for any:
 - a. Anticoagulant (dabigatran, rivaroxaban, apixaban) or
 - i. Date
 - b. P2Y12 Antagonists (clopidogrel, prasugrel or ticagrelor) without a new diagnosis of acute coronary syndrome
 - i. Date
4. Other AF-related therapies (i.e. antiarrhythmic agents excluding beta-blockers and calcium channel blockers, cardioversions, ablation procedures or hospitalizations with a primary diagnosis of AF)
5. UtilizationCommented [[name]]: Need to further define
3. Stroke-related visits during follow-up [Aetna Medical Case]
 - a. Inpatient
 - b. ER
 - c. Time to first stroke-related event (Inpatient or ER)
4. Myocardial infarction-related visits during follow-up [Aetna Medical Case]
 - a. Inpatient
 - b. ER
 - c. Time to first myocardial infarction-related event (Inpatient or ER)
5. Systemic thromboembolism-related visits during follow-up [Aetna Medical Case]
 - a. Inpatient
 - b. ER
 - c. Time to first systemic thromboembolism-related event (Inpatient or ER)
6. Death (Medicare population): [Aetna ATV; Aetna Membership Table]
 - a. Time to death (within 1 month of date)

- b. Cause of death
- 7. All-Cause Hospital Admissions [Aetna Medical Case]
 - a. Total number
 - b. Total length of stay
 - c. Individual admissions
 - i. Primary diagnosis
 - ii. Date
 - iii. Length of stay

Safety Endpoints

- 1. Hospital admission for primary bleeding diagnosis: [Aetna]
- 2. Incidence of non-AF, but other actionable heart rhythms captured by device (and confirmed by PI) [PI Diagnostic Database]
 - a. Atrial Tachycardia with variable block of > 30 seconds
 - b. Ventricular Tachycardia >5 beats
 - c. Pauses \geq 5 seconds
 - d. AV block
- 3. Early discontinuation of active monitoring in monitored cohort [Scripps Study Database]
 - a. Date of discontinuation
 - b. Cause of discontinuation

Exploratory Endpoint (Amiigo)

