The analysis will compare the proportion of subjects with newly diagnosed atrial fibrillation (numerator) per number of total number of subjects in group (denominator) during the first 12 months from the date of enrollment of the actively monitored subject between the actively monitored cohort and matched observational cohort using Fisher's exact test. Multivariable analysis of the AF/atrial flutter outcome will also be performed using binomial multivariable logistic regression models to include baseline demographic (age, sex, race/ethnicity, median household income, geography, insurance type), co-morbidity covariates. The same analysis will be performed for the other 12-month follow-up outcomes of new prescription for anticoagulation medication and new prescription of other AF-related medications. All analyses will be conducted first as intention-to-treat and second among the per-protocol population.

Matched Observational Cohort Study – 3 year Follow-up

Analyses at 3 years of follow up will focus on time to event for disease outcomes (stroke, myocardial infarction, and systemic thromboembolism) and hospitalizations (all-cause and for bleeding) compared between the actively monitored cohort and the matched observational control cohort after 3 years of follow-up. Bivariate time-to-event analysis will be conducted using Kaplan-Meier analysis with the time to event calculated from the date of the enrollment of the actively monitored subject and the date of the first event of the specific disease outcome (separate analysis for each outcome). Subjects not having an endpoint event during the observation period will be censored at the end of the 3-year follow-up or date of discontinued enrollment from Aetna. Multivariable analyses will be conducted using Cox proportional hazard models and will include potential confounders including age, sex, race/ethnicity, insurance type, variables related to geography and co-morbidity scores. For the Cox models, if assumptions of proportionality are not met (as assessed by Kaplan-Meier and plots of Schoenfeld residuals), models accounting for non-proportionality (using time*covariate interaction terms) will be run.

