We will use the same time to event analyses with 3 year follow-up to evaluate the same disease and hospitalization endpoints among the subset of subjects included in the matched observational cohort study who receive a diagnosis of atrial fibrillation during the study. All analyses will be performed as intention-to-treat with parallel exploratory analyses performed on per-protocol basis restricted to subjects enrolled in the monitoring group who underwent Zio patch monitoring.

Analysis of Safety Endpoints

For analysis of safety endpoints at 3 year follow-up, we will compare incidence of hospitalization for bleeding per person-years of follow-up between the actively monitored group and the matched observational control group. Hospitalizations for bleeding will also be characterized by length of stay. Other safety outcomes will be characterized for the period of active monitoring in the active monitoring group only. These include Incidence of non-AF, but other actionable heart rhythms captured by the Zio patch device, specifically: 1) Atrial Tachycardia with variable block of > 30 seconds; 2) Ventricular Tachycardia >5 beats; 3) Pauses \geq 5 seconds; and 4) AV block. We will also characterize early discontinuation of active monitoring in monitored cohort by cause and time to event.

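### The 3-year analyses in people diagnosed with AF select on a post-enrolment diagnosis that is found differently in each cohort, so screening can look protective when it has no effect

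*SAP*

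**What the plan says.** SAP section 3 lists secondary items 8 to 12 and safety item 1 in two forms: (a) in the entire cohorts and (b) "In the sub-population of individuals newly diagnosed with AF during the 3-year follow-up". SAP section 4 (Atrial Fibrillation Sub-population) admits monitored members through the patch or claims, but for controls the group is "subjects in the matched observational control cohort who received a new diagnosis of atrial fibrillation based on claims data during the 3 year follow-up". Protocol section 4 (Atrial Fibrillation Diagnosis) agrees: "For the control cohort a new diagnosis will be based solely on a new clinical diagnosis documented in claims data".

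SAP section 7 (3 year Follow-up) applies the same analyses "among the subset of subjects included in the matched observational cohort study who receive a diagnosis of atrial fibrillation during the study", with "time to event calculated from the date of the enrollment of the actively monitored subject". SAP section 4 starts outcome ascertainment on that date for both cohorts, so the hospitalization count in 12b has the same window. Sections 7 and 8 contain no landmark, delayed entry, time-dependent diagnosis or rule for events on or before diagnosis. The only sensitivity analysis concerns how matching is handled.

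The one 3-year power figure (Protocol section 7; SAP section 7, Sample Size Determinations) is for this subset: 81% with 200 versus 400 people and event rates of 5% versus 12%. The SAP does not say whether the (a) or the (b) analyses carry the 3-year conclusion.

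**The concern.** Membership of the subset depends on what happens after time zero, through a process that differs by cohort. A control with silent AF who has a stroke may be found to have AF during that admission, and then enters the subset with the event already counted. A control with silent AF and no event may never be diagnosed, and then leaves the denominator. Patch screening brings many such event-free people into the monitored subset. The control event rate is inflated relative to the monitored rate even if screening does nothing.

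Fatal events push the other way. Item 8 ("Compare time to first event of the combined endpoint of stroke, systemic embolism, or myocardial infarction in the actively monitored cohort") does not exclude fatal events. A person who dies of the event before any AF diagnosis drops out of the subset, and this happens mostly among controls, who are diagnosed later. Item 9 adds death, so 9b is the most exposed to this reversal.

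At stake is the reading of a significant (b) result. It could be reported as a benefit of screening when part of it comes from how the subset was formed, and no planned table would let a reader separate the two.

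**Working it through.** **1. The plan's own power figure.** Inputs: 200 and 400 people, 5% and 12%, two-sided 0.05. The pooled rate is (10 + 48)/600 = 0.0967. The null standard error is √[0.0967 × 0.9033 × (1/200 + 1/400)] = 0.0256; the alternative one is √[0.05 × 0.95/200 + 0.12 × 0.88/400] = 0.0224. Power = Φ[(0.07 − 1.96 × 0.0256)/0.0224] = 0.81. The stated figure reproduces as a comparison of two proportions; a simulated log-rank test gives 0.83. Neither calculation models how the subset is formed.

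**2. Null model, all events survived.** Everyone with latent AF has a 12% 3-year event risk (the plan's control rate), and screening has no effect. Let C be the share diagnosed by 3 years irrespective of events and q the probability that a survived event triggers a diagnosis. Both are assumptions. Then:

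- selected with an event: 0.12 × [C + (1 − C)q]
- selected without an event: 0.88 × C
- subset risk r = first line ÷ sum of the two lines
- HR ≈ ln(1 − r_monitored)/ln(1 − r_control)

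Take control C = 0.7 and q = 0.5. Controls: 0.12 × 0.85 = 0.102 and 0.88 × 0.7 = 0.616, so r = 0.102/0.718 = 14.2%. Two monitored curves were used:

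- Curve A, the protocol's planning curve (100% complete): r = 12.0%, HR = 0.1278/0.1532 = 0.83.
- Curve B, patch finds half and the rest follow the control curve (0.5 + 0.5 × 0.7 = 85% complete): 0.111/(0.111 + 0.748) = 12.9%, HR = 0.1384/0.1532 = 0.90.

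**3. Adding fatal events.** These need diagnosis timing, so they were simulated, with control diagnosis following the shape of the protocol's 3-year table scaled to C. A fatal event counts only if AF had already been diagnosed. Null HRs at control C = 0.7 (curve A / curve B):

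| q | none fatal | 10% fatal | 25% fatal |
|---|---|---|---|
| 0.25 | 0.91 / 0.95 | 0.93 / 0.97 | 0.98 / 1.02 |
| 0.5 | 0.83 / 0.90 | 0.86 / 0.93 | 0.91 / 0.97 |
| 1 | 0.72 / 0.83 | 0.74 / 0.86 | 0.79 / 0.91 |

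Falsely significant protective results at q = 0.5 (5,000 trials of 200 and 400; nominal 2.5%): 9.9% / 4.9% with none fatal, 6.9% / 4.4% with 10% fatal, 4.5% / 3.0% with 25% fatal.

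**4. Where the bias vanishes or reverses.**

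- q = 0, none fatal: HR 0.99 to 1.00 at every C.
- C = 0.9, q from 0.25 to 1: 0.90 to 0.99 with none fatal, 0.97 to 1.06 with 25% fatal.
- C = 1: about 1.0 with none fatal, 1.06 to 1.08 with 25% fatal. Check on curve A: with even spacing within intervals, the protocol's table puts mean time to diagnosis at 20.6 of 36 months in controls (57%) and 11.25 in the monitored cohort (31%). Counted events are 0.09 + 0.03 × 0.43 = 0.103 and 0.09 + 0.03 × 0.69 = 0.111, risks 10.5% and 11.2%, HR about 1.07.
- 9b at C = 0.7, q = 0.5: 1.03 to 1.09 if half of events are fatal, 1.61 to 1.66 if all are.

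**5. A different model.** With latent AF at 14%, screening finding 45% of it and clinical diagnosis at 0.30 per year (all assumed), null HRs were 0.92, 0.86 and 0.82 at q = 0.25, 0.5 and 0.75. The same model without selection on diagnosis gave 0.99 to 1.01.

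**6. What the planning table shows about timing.** For 400 controls it implies 16, 36 and 48 events against 20, 120 and 400 diagnoses at 6, 15 and 36 months. These are marginal counts and allow anywhere from 0 to 48 events before diagnosis. With even spacing and independence the share is (4 × 0.975 + 5 × 0.825 + 3 × 0.35)/12 = 76%, about 36 of 48. That is suggestive only and does not measure the bias.

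**7. Entire-cohort power.** Use the plan's AF-subset rates, 10% AF, and an assumed 3% 3-year risk in people without AF. Monitored: 0.1 × 0.05 + 0.9 × 0.03 = 3.2%; control: 0.1 × 0.12 + 0.9 × 0.03 = 3.9%. HR 0.82; events 2000 × 0.032 + 4000 × 0.039 = 220. Power = Φ[√(220 × 2/9) × |ln 0.82| − 1.96] = 0.29, taking the HR unrounded. At 6% it is 0.19 and at 9% about 0.15.

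**The case against.** The strongest reply is that the plan assumes 10% diagnosed AF in both cohorts by 3 years. With that catch-up there is no protective bias, and with some fatal events the tilt is against screening. This stands as arithmetic, but equal totals are a planning assumption that nothing in the analysis secures. Nor do the documents supply control completeness: the protocol's figure ("Based on prior studies supporting that 30% of the total AF population is undiagnosed") is a cross-sectional share of all AF, so 70% is illustrative.

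Second, the larger effects pair a 70% control curve with a monitored curve that reaches 100%. After patching ends, monitored members also rely on claims, so curve B is the more coherent. This is fair. On curve B the false-protective rate is 3.0% to 4.9% at q = 0.5, and a repeat run gave 2.5% to 5.7%.

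Third, counting from enrolment fits the rationale that earlier diagnosis prevents events. True, and the clock alone does no harm when q = 0 and no event is fatal. The fault lies in combining it with selection on later diagnosis.

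Fourth, 12b is a count, and the SAP's safety paragraph describes bleeding per person-years by cohort. Both still use the selected subset under section 3, but no size is estimated for 11b, 12b or safety 1b.

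Fifth, each subset analysis has an entire-cohort companion. That limits the damage, but no hierarchy is stated and the only 3-year power belongs to the subset. The companions also have low power, which depends on the assumed non-AF rate: at 1% it would be about 53%.

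**Conclusion.** The concern holds. The subset is formed by a post-enrolment diagnosis, ascertained differently by cohort, analysed from enrolment, with no safeguard. Under no true effect the subset hazard ratio for 8b can fall below 1: 0.83 to 0.90 at 70% control completeness, q = 0.5 and no fatal events, or 0.91 to 0.97 with 25% fatal. It can also be about 1 or, especially for 9b, above 1. Completeness, q and case fatality are all assumed, so neither size nor direction can be fixed from the documents. These are secondary, non-randomised analyses and the randomised 4-month primary endpoint is untouched. The point should be fixed before the 3-year data are analysed; confidence in its practical size is moderate.

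**What to change.** Amend the SAP as follows.

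- State that 3-year inference rests on the entire-cohort analyses already listed (8a to 12a, safety 1a). Note that they compare consenting volunteers, about 5% of those approached, with matched members who were never invited, so they rely on the matching and covariate adjustment.
- Label 8b to 12b and safety 1b descriptive.
- Add one table, by cohort, of events before or at AF diagnosis and events after it.
- If a time-to-event display is kept for the subset, start it at AF diagnosis in people event-free at that point. In the null simulation at 70% completeness this gave HRs of 0.99 to 1.01. Say that it omits the events earlier diagnosis is meant to prevent and leaves lead-time and case-mix differences.
- State that the 81% power applies only to the AF subset, and add entire-cohort power.

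The cost is SAP wording and one table, with no new data. The downside is a less favourable stated 3-year power: about 15% to 29% if the 3-year event rate in members without AF is 9% down to 3%, a range the documents do not give.
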